Appendix 5. SAS Code for the Generalized Linear Mixed Model for Binary Longitudinal Data

```
PROC GLIMMIX DATA =<DATA> METHOD=RMPL;  
  CLASS SUBJID TRTPN VISIT;  
  MODEL RESPONSE (EVENT = "1") = TRTPN VISIT TRTPN * VISIT / ALPHA = 0.1  
  DIST=BINARY LINK=LOGIT;  
  RANDOM VISIT /SUBJECT = SUBJID TYPE=UN RESIDUAL;  
  LSMEANS TRTPN * VISIT / ILINK COV DIFF CL;  
RUN;
```

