5.2. General Methods

5.2.1. Analyses for Binary Endpoints

Landmark (cross-sectional) analyses of key binary endpoints will calculate and test for risk differences using the method of (Chan and Zhang 1999).² Covariates will not be included in the primary analyses. Risk differences and 90% confidence intervals will be presented.

For all key binary endpoints such as PASI75, PASI90 and PGA scores etc that are measured repeatedly over time, will be analyzed using generalized linear mixed effect model (GLMM) with treatment group (defined as factor variable), visit, treatment group by visit interaction and subjects as the random effect. An unstructured covariance matrix will be used to fit such model. In case, if the model fails to converge, a covariance structure such as compound symmetry or autoregressive model may be used. Bayesian information criterion (BIC) will be used to assess the goodness of fit of the models. The model with the smallest BIC will be selected for inference. P-values and inference for relative risks between treatments will be provided based on the link function of logit.

For all binary endpoints, a summary based on the mITT Observed Efficacy Set of the number of subjects in each category based on observed cases in each treatment arm at each time point will be produced and the response rate will also be plotted against time, by treatment group.

Exploratory categorical analyses that include or assess the effects of covariates may be done on an exploratory basis. Exploratory longitudinal analyses may also be performed including appropriate covariates of interest.

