6.1.1.2. Sensitivity/Supplementary Analyses

- Estimand strategy: Primarily this estimand is intended to provide an estimate of the treatment effect in the population level assuming missing data are either MCAS (Missing Completely at Random) or MAR (Missing at Random). Applicable statistics will be calculated at Week 16.
- Population: mITT.
- Analysis methodology: GLMM and descriptive statistics.
- Missing Data: Observed Data.

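### SAP 5.2.1 describes a subject random-effect model chosen by BIC, but Appendix 5 codes a marginal pseudo-likelihood model, so the GLMM sensitivity analyses have two possible targets and a covariance rule that does not suit the code.

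*SAP*

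**What the plan says.** SAP 5.2.1 (Analyses for Binary Endpoints) says that repeatedly measured binary endpoints will be analysed by a generalized linear mixed effect model containing treatment group, "visit, treatment group by visit interaction and subjects as the random effect". On covariance it says "An unstructured covariance matrix will be used to fit such model", then "In case, if the model fails to converge, a covariance structure such as compound symmetry or autoregressive model may be used", and then "The model with the smallest BIC will be selected for inference". On the effect measure it says "P-values and inference for relative risks between treatments will be provided based on the link function of logit".

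SAP Appendix 5, headed as the code for this model, opens with "PROC GLIMMIX DATA =<DATA> METHOD=RMPL". Its only RANDOM statement is "RANDOM VISIT /SUBJECT = SUBJID TYPE=UN RESIDUAL". It requests treatment-by-visit least-squares means, their differences on the logit scale, and inverse-linked probabilities. It has no statement that produces a relative risk.

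SAP 6.1.1.2 assigns the GLMM, on observed data, to the sensitivity/supplementary analysis of PASI 90 at Week 16, where "this estimand is intended to provide an estimate of the treatment effect in the population level". SAP 6.2.1.2, 6.2.2.2 and 6.2.5.2 use it in the same role for PASI 75, PGA and the other binary endpoints. Nothing in either document says whether the text or the code takes precedence.

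**The concern.** In PROC GLIMMIX the RESIDUAL option turns a RANDOM statement into a within-subject error covariance (R-side). It does not add a random effect. With no other RANDOM statement, the coded model has no subject effect, and RMPL is restricted marginal pseudo-likelihood. The code therefore estimates a population-average effect. A model with a random subject effect, as the text describes, estimates a subject-specific effect. With a logit link these are different numbers unless the subject variance is close to zero.

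The selection rule has a separate problem. Pseudo-likelihood works on linearised pseudo-data that are rebuilt from the current fit, so each covariance structure ends up with its own pseudo-data. A BIC from one structure is then not on the same footing as a BIC from another.

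What is at stake is reproducibility and interpretation. Two programmers could each claim to follow the SAP and report clearly different odds ratios or relative risks. If the unstructured fit fails, the SAP gives them no valid rule for choosing between the fallbacks.

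**Working it through.** The plan states no figure for this model, so there is none to reproduce. There are two checks.

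**1. How far apart are the two targets?**

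Inputs: placebo PASI 90 rate 5% and a placebo-corrected effect of 35 points, giving 40% on active (Protocol 9.2). Assumptions: the text is read as a random-intercept logistic model, and the subject SD σ on the logit scale is 1, 2 or 3. The documents give no value for σ.

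- Marginal model (Appendix 5): OR = (0.40/0.60)/(0.05/0.95) = 12.7; RR = 0.40/0.05 = 8.0; RD = 0.40 − 0.05 = 0.350.
- Random-intercept model (5.2.1): for each arm solve E[expit(η + σZ)] = p for η, with Z standard normal and p = 0.05 or 0.40, by 60-point Gauss-Hermite quadrature. Then OR = exp(η_active − η_placebo). The inverse-linked estimates are expit(η), taken at a zero random effect. RR and RD are formed from these.

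| σ | η placebo, active | log OR | OR | inverse-linked % | RR | RD |
|---|---|---|---|---|---|---|
| 0 (marginal) | −2.944, −0.405 | 2.539 | 12.7 | 5.0, 40.0 | 8.0 | 0.350 |
| 1 | −3.372, −0.490 | 2.882 | 17.8 | 3.3, 38.0 | 11.4 | 0.347 |
| 2 | −4.422, −0.668 | 3.755 | 42.7 | 1.2, 33.9 | 28.6 | 0.327 |
| 3 | −5.758, −0.880 | 4.878 | 131 | 0.3, 29.3 | 93 | 0.290 |

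RR and RD use unrounded probabilities. Every row describes the same population rates; only the model differs.

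**2. Can BIC choose between structures here?**

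Three trials were simulated with 40 per arm, three visits, σ = 2 and dropout at random. Each was fitted by restricted marginal pseudo-likelihood with unstructured (UN), compound symmetry (CS) and autoregressive (AR(1)) covariance.

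- The pseudo-data for the same observations differed between structures by up to 0.5 to 1.7 on the logit scale, so the criteria are computed on different data.
- In one trial CS, which is nested in UN, had the smaller −2 log pseudo-likelihood (1080.3 against 1082.5). A true likelihood maximised on fixed data cannot do that.
- The Week 16 odds ratio changed little between structures: 6.5–7.5, 17.8–18.2 and 16.2–16.4 in the three trials.

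This was a purpose-written implementation with a capped number of iterations, not SAS. The argument rests on the changing pseudo-data; the single reversed value only illustrates it.

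The rule may well be needed. The Schedule of Activities has seven post-baseline visits to Week 16, so UN has 7 × 8/2 = 28 covariance parameters. Arms have 20 or 40 participants, and 40 × 0.05 = 2 placebo responders are expected at Week 16. Non-convergence is a realistic prospect.

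**The case against.** The strongest reply is that most of the SAP already points to the coded model. UN, CS and autoregressive structures describe covariance over visits, whereas a single subject intercept has only one variance. Section 6.1.1.2 asks for a population-level effect, and the code is explicit. On this view one loose phrase is out of place. That is a fair reading and it decides the direction of the repair. It does not remove the conflict, because the phrase describes a different model and no order of precedence is given.

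The BIC rule can also be read narrowly: UN is fitted first, and BIC matters only among fallbacks if UN fails. That stands and limits when the rule applies, but in that case the comparison is still not valid.

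The odds-ratio gap reflects non-collapsibility at an assumed SD, both models share the same null, and the main analysis reports risk differences, which differ little at SD 1. All of that stands. However, 5.2.1 promises relative risks, and on that scale the gap is 8.0 against 11.4 even at SD 1.

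Four stronger readings are tempting and are not supported:

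- **That this is the only sensitivity analysis of the primary endpoint.** Protocol 8.1.1 also plans one using the linear-scaled PASI, and SAP 4.4 and 4.5 mention others.
- **That p-values are distorted by the choice of structure.** In simulations at 40 vs 40 and 20 vs 40 (σ = 2 assumed, UN not fitted, runs with empty cells dropped), model-based standard errors differed between CS and AR(1) by a median of 1.4% and 1.1%. One-sided 5% rejection under a 20% vs 20% null was 4.9% and 5.3%.
- **That a robust variance would make the standard errors independent of the structure.** In the same runs the robust errors differed more, by 3.0% and 2.6%.
- **That the marginal model is biased under missing at random.** A large simulation with an exchangeable marginal fit returned 40.1% against a true 40%.

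**Conclusion.** The point holds as a mismatch between SAP text and code, together with a selection rule that is not valid for the coded estimator. Followed literally, 5.2.1 gives a subject-specific effect, contrary to the population-level aim of 6.1.1.2.

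The size depends on scale and on an assumed subject SD. On the odds-ratio and relative-risk scales the gap is material across SD 1 to 3. On the risk-difference scale it is negligible at SD 1 and reaches 0.06 (0.350 − 0.290) at SD 3. The two readings agree only when the subject variance is near zero. The subject-specific relative risks assume that they are formed from inverse-linked estimates at a zero random effect.

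The reach is limited to the GLMM sensitivity/supplementary analyses of PASI 90, PASI 75, PGA and the other binary endpoints. A reader might infer that the trial's conclusion is at risk. It is not: the primary test is the Chan and Zhang exact analysis with Hochberg control (SAP 5.1 and 6.1.1.1), and no success criterion uses the GLMM. This should be corrected, but it does not undermine the primary result.

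**What to change.** Keep the marginal model in Appendix 5, since it matches the aim in 6.1.1.2, and bring 5.2.1 into line with it:

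- Delete the words that make subject a random effect, and say that the model is population-average with within-subject covariance over visits.
- Delete the BIC sentence. State a fixed order using the structures already named: UN first, then compound symmetry, then autoregressive, moving on only when a fit does not converge.
- Optionally, add a small-sample-corrected robust variance as protection against a misspecified fallback structure. It should not be described as making the standard errors independent of the structure.

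The cost is a few sentences in the SAP and, if the optional step is taken, one code option. No data collection, sample size or primary analysis changes. It should be done before unblinding, so that the model is not chosen with results in view.

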Appendix 6. SAS Code for Estimand 1 – Risk Difference using (Chan and Zhang 1999)²

```
PROC BINOMIAL DATA=<DATASET> GAMMA=0 ALPHA=<Value>;
```

```
PD/EX ONE STD;
```

```
PO <POPULATION VARIABLE>;
```

```
OU <OUTCOME VARIABLE>;
```

```
RUN;
```

**Appendix 7. SAS Code for the Confidence Interval of a Binomial Proportion
(Blyth-Still-Casella)**

```
PROC BINOMIAL DATA=<DATASET> ALPHA=<value>;
```

```
BI/BS;
```

```
OU <RESPONSE VARIABLE>;
```

```
RUN;
```

Appendix 8. List of Abbreviations

Abbreviation	Term
Abs	absolute
AE	adverse event
ANCOVA	analysis of covariance
ANOVA	analysis of variance
ATC	Anatomic Therapeutic Chemical
AUC	area under the curve
BA	bioavailability
BE	bioequivalence
BIC	Bayesian information criterion
BLQ	below the limit of quantitation
BOCF	baseline observation carried forward
BP	blood pressure
BSA	Body Surface Area
CDARS	Clinical Data Analysis and Reporting System (of US Food and Drug Administration)
CDISC	Clinical Data Interchange Standards Consortium
CI	confidence interval
C _{max}	maximum observed concentration
CMH	Cochran-Mantel-Haenszel
CRF	case report form
CSR	clinical study report
CCI	
DMC	data monitoring committee
EAC	event adjudication committee
ECG	electrocardiogram
E-DMC	external data monitoring committee
FAS	full analysis set
FCS	full conditional specification
FDA	Food and Drug Administration (United States)
GCP	Good Clinical Practice
GLIMMIX	generalized linear mixed-effects model with repeated measures
GLMM	generalized linear mixed effect model
GMC	geometric mean concentration
GMFR	geometric mean fold rise
GMR	geometric mean ratio
GMT	geometric mean titer
HDL	high density lipoprotein
ICD	informed consent document
ICH	International Council for Harmonisation
IRC	internal review committee
IST	independent statistical team

Abbreviation	Term
ITT	intent-to-treat
LDL	low-density lipoprotein
LLOQ	lower limit of quantitation
LOCF	last observation carried forward
LOD	limit of detection
LS	least-squares
LSM	least-squares mean
MAR	missing at random
MCAS	Missing Completely at Random
MedDRA	Medical Dictionary for Regulatory Activities
mITT	modified intent-to-treat
MMRM	mixed-effects model with repeated measures
MNAR	missing not at random
N/A	not applicable
NNB	number needed to benefit
NNH	number needed to harm
NNT	number needed to treat
NOAEL	no-observed-adverse-effect level
CCI [REDACTED]	[REDACTED]
OC	observed case
PASI	Psoriasis Area Severity Index
PD	pharmacodynamic(s)
PGA	Physician Global Assessment
PK	pharmacokinetic(s)
CCI [REDACTED]	[REDACTED]
PP	per-protocol
PPAS	per-protocol analysis set
PP-NRS	Peak Pruritus Numerical Rating Scale
PRO	patient-reported outcome
PT	preferred term
CCI [REDACTED]	[REDACTED]
QoL	quality of life
QTc	corrected QT
QTcF	corrected QT (Fridericia method)
qual	qualitative
RCDC	reverse cumulative distribution curve
RR	relative risk
SAE	serious adverse event
SAP	statistical analysis plan
SAS	safety analysis set
SD	standard deviation
SGS	Statistical Guidance Standards
SoA	schedule of activities

Abbreviation	Term
SOP	standard operating procedure
SUSAR	suspected unexpected serious adverse reaction
TA	therapeutic area
TEAE	Treatment-Emergent Adverse Event
ULN	upper limit of normal
WHO	World Health Organization
WHODD	World Health Organization Drug Dictionary
